4.3.2. Selection of FAPI-46 for development

[figure not shown]
Because of these improved and continued promising results with FAPI-04, further optimization to enhance tumor retention while maintaining high image contrast was identified, needed and feasible. As an extension to their early work noted above, [Loktev et al. 2019](#) developed and tested fifteen additional FAPI compounds which identified FAPI-46 as having marked improved performance, including better tumor uptake and higher tumor-to-organ ratios compared to FAPI-04, confirming FAPI-46 as the preferred, optimal compound for FAP PET imaging.

In addition to the work aimed at optimizing FAPI-compounds, several non-clinical *in vitro* and *in vivo* studies have been conducted to specifically investigate FAPI-compounds in pancreatic cancer. [Loktev et al. 2019](#) and [Watabe et al. 2020](#) demonstrated negligible binding of FAPI to the human pancreatic ductal adenocarcinoma (PDAC) cell lines BxPC3, Capan-2, PANC-1 and MIA PaCa *in vitro*. Conversely, in mice bearing subcutaneous Capan-2, PANC-1 or MIA PaCa tumors, [⁶⁸Ga]FAPI tumor uptake was confirmed and may be explained by the recruitment and subsequent activation of mouse fibroblasts. As expected, immunohistochemistry showed FAP expression in the stroma of these xenografts. Lastly, a PDAC patient-derived xenograft and orthotopically implanted KP4662 PDAC tumors were imaged using [⁶⁸Ga]FAPI-46 and exhibited tumor uptake matched by FAP positivity in the stroma per immunohistochemistry (unpublished data, University of California Los Angeles [UCLA]).

4.3.3. Investigational Product Overview

The investigational product is [^{68}Ga]FAPI-46.

4.3.4. Structure:

4.3.5. Synthesis

FAPI-46 precursor is a small molecule critical drug intermediate consisting of a FAPI moiety conjugated with a DOTA chelator for use in manufacturing the radiolabeled final drug product. FAPI-46 precursor is supplied in single use vials ($0.050 \text{ mg} \pm 20\%$) from ABX in powder form. The radionuclide in this study, gallium-68, is a neutron deficient isotope (31 neutrons and 37 protons) of gallium which decays via electron capture and positron emission to zinc-68. Gallium-68 has a 68-min. half-life, with a relatively low translational energy of the positron (1.9 MeV) for producing high quality positron emission tomography (PET) images. FAPI-46 precursor is reacted with gallium-68 to produce the final drug product [^{68}Ga]FAPI-46. The resulting material contains buffering excipients that maintain the stability to produce the [^{68}Ga]FAPI-46 final drug product. [^{68}Ga]FAPI-46 final drug product will be manufactured and tested by Sofie Network Inc.

4.4. Nonclinical and Previous Clinical Studies Overview

See Investigational Brochure for additional information.

Preclinical studies by [Loktev et al. 2019](#) established that FAPI-46 as an extremely promising PET tracer with high binding specificity and selectivity to FAP-expressing cells, with high tumor-to-healthy tissue contrast. Radiolabeled FAPI-46 serum stability study showed that at 24 hours only the intact radioactive drug was detected with neither radioactive degradation products nor free radioactivity being observed or measured, supporting *in vivo* stability in human sera. In cell culture experiments, FAPI-46 was incubated with cells to assess binding affinity and specificity. FAPI-46 was shown to exhibit strong binding to HT-1080-hFAP cells with an EC_{50} of 13.5 nM. Negligible binding was noted in a cell line not expressing FAP.

In vivo pharmacodynamic studies were conducted to demonstrate *in vivo* and *ex vivo* biodistribution, as well as *in vivo* binding specificity. *In vivo* and *ex vivo* biodistribution data were highly congruent with a high tumor: blood, tumor: liver and tumor: muscle ratios. Binding specificity was confirmed *in vivo*, whereby the addition of unlabeled compound competitively blocked all [^{68}Ga]FAPI-46 accumulation in tumors.

A single dose, acute and extended, Good Laboratory Practice (GLP) compliant toxicology study was performed. A single dose of [$^{\text{nat}}\text{Ga}$]FAPI-46 ($166.7 \text{ } \mu\text{g/kg}$) was administered intravenously to male and

female rats. Acute and delayed toxicity evaluations were performed. The dose was well-tolerated and no adverse effects were noted. The human equivalent dose (HED) was preselected as 100 µg for a 60 kg adult which is 100 x of the no observed adverse effect level (NOAEL) established in rats.

Data regarding the safety, dosimetry and efficacy of [⁶⁸Ga]FAPI-46 in humans have been extracted from published literature and has been received as personal communications from cited investigators and institutions. [⁶⁸Ga]FAPI-46 has been evaluated for biodistribution and dosimetry [Meyer et al, 2019]. [⁶⁸Ga]FAPI PET/CT imaging was shown to be safe for administration up to at least 200 MBq (5.4 mCi) [Meyer et al., 2019]. At 200 MBq (5.4 mCi), the whole-body effective dose including CT is 5.3 mSv, with CT contributing 3.7 mSv. Next, biodistribution was assessed for two of the six patients (one male and one female) [Meyer et al, 2019]. The highest average normal organ SUVmax at all time points was for the liver.

Tracer uptake in the tumor was rapid and had a greater retention time than normal organs; however, both mean SUVs decreased in all patients from the first to the last time points and tumor-to-background ratios increased over time. Therefore, in the totality of all the data, it was clearly determined that [⁶⁸Ga]FAPI-46 has a favorable dosimetry, avidity, and diagnostic isotope labeling profile with a biodistribution profile amenable for detection of FAP- expressing cells in patients with PDAC.

Lastly, but importantly, from preliminary diagnostic patient studies to date, there have been > 200 [⁶⁸Ga]FAPI-46 PET/CT scans with no reported adverse events [[name], Personal Communication. Essen University Hospital].

4.5. Rationale for this Study

As a diagnostic radiopharmaceutical at minute tracer amounts, the very favorable dosimetry and non-toxic molecular design, a very robust benefit/risk and safety profile is expected and will be studied and confirmed during further product development.

5. STUDY OBJECTIVES AND ENDPOINTS

5.1. Objectives

5.1.1. Primary Objective

- Evaluate the performance [sensitivity, specificity, accuracy] of [⁶⁸Ga]FAPI-46 PET imaging to detect FAP-expressing cells, using histopathology as truth standard.

5.1.2. Secondary Objectives

- Evaluate positive and negative predictive values of [⁶⁸Ga]FAPI-46 PET images, to detect FAP-expressing cells, using histopathology as truth standard.
- Correlate the histopathology with FAP staining on FAP IHC assay.
- Further characterize the safety profile of [⁶⁸Ga]FAPI-46 in patients with PDAC

5.1.3. Exploratory Objectives

- Compare the detection of local and metastatic disease using [⁶⁸Ga]FAPI-46 PET to a composite of clinical, radiological (i.e. CT, MR), and histopathological reference in

patients with resectable or borderline resectable PDAC.

- Compare pre- and post-treatment [^{68}Ga]FAPI-46 PET evaluations obtained in Cohort 2 to identify perturbations, if any, from neoadjuvant therapy treatment.

5.2. Endpoints

5.2.1. Primary Efficacy Endpoint

- Sensitivity, specificity, and accuracy will be determined on a per-lesion basis for all lesions with tissue available for analysis.
 - Lesions positive for FAP as detected by [^{68}Ga]FAPI-46 PET imaging
 - Malignant lesions as detected by histopathology

5.2.2. Secondary Efficacy Endpoints

- Positive and negative predictive value will be determined on a per-lesion basis for all lesions with tissue available for analysis.
 - Lesions positive for FAP as detected by [^{68}Ga]FAPI-46 PET imaging
 - Malignant lesions as detected by histopathology
- Staining intensity assessed by immunohistochemistry, using H-score, correlated to the uptake of [^{68}Ga]FAPI-46, using SUV_{max} .
 - Lesions positive for FAP as detected by immunohistochemistry

5.2.3. Exploratory Efficacy Endpoints

- Number of malignant lesions (local, metastatic) identified through anatomical (i.e., CT, MR) and/or [^{18}F]-FDG PET
- Number of [^{68}Ga]FAPI-46 identified lesions and the radiotracer accumulation observed in local and metastatic disease using SUVPercentage change in [^{68}Ga]FAPI-46 PET imaging using SUV levels and number of identified lesions between pre- and post-neoadjuvant therapy.

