6.2.3 Exploratory Efficacy Measures

The exploratory endpoints to be analyzed include:

- Number of lesions identified (0, 1, 2, 3 or more) through Standard of Care (anatomical (ie, CT, MR) and/or [¹⁸F]-FDG PET) and [⁶⁸Ga]FAPI-46 images
- Radiotracer accumulation observed in identified lesions SUV_{max}, SUV_{mean}, and tumor-to-background ratio (TBR) . If different background regions (such as muscle, blood, etc...) are used, TBR will be calculated and presented for all of them.
- Percentage change in [⁶⁸Ga]FAPI-46 PET SUV_{max} in the primary lesion between pre- and post-neoadjuvant therapy

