7.1.2.3 Efficacy Analysis Set 3 (EFFS3)

All patients from Cohort 1 and Cohort 2 who received [⁶⁸Ga]FAPI-46, have interpretable FAPI-46 PET and standard of care images (ie, CT or MRI or [¹⁸F]-FDG PET).

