10.6.5 Exploratory Analyses

All exploratory analyses will be conducted on the efficacy population defined for each analysis, and will be summarized by cohort, visit, and, where applicable, by region. The data for these presentations will be obtained from the following eCRFs (and associated imaging results):

- Non – Target/Non-Index Lesions
- Target/Index Lesions

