10.6.5.1 PET Intensity

Descriptive analyses will be performed on PET intensity parameters and the following summaries will be produced:

- SUV_{max}, SUV_{mean}, and TBR in identified lesions using PET scan (EFFF1).
- SUV_{max}, SUV_{mean}, and TBR in identified lesions using PET scan and correlated with conventional [¹⁸F]-FDG PET scan for the same lesion if data is available. The correlation between [⁶⁸Ga]FAPI-46 PET and [¹⁸F]-FDG PET scan will be analyzed by Pearson's correlation test. The correlation coefficient and 95% CI will be provided (EFFF3).
- SUV_{max}, SUV_{mean}, and TBR differences between pre-NAT and post-NAT in the primary lesion for Cohort 2 using PET scan (EFFF4).

10.6.5.2 Tumor Lesions Detected by [⁶⁸Ga]FAPI-46 PET in Comparison with CT/MRI and/or [¹⁸F]-FDG PET

In addition to the primary lesion, a maximum of 3 LN was assessed by the reader. The number of identified LN detected by [⁶⁸Ga]FAPI-46 PET scan versus the standard of care assessments CT/MRI and/or [¹⁸F]-FDG PET, will be presented for the EFFF3 by cohort and visit, including pre-NAT and post-NAT differences for Cohort 2.

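### The exploratory comparison of FAPI-46 with standard-of-care detection is specified as node counts per modality, with no within-patient table, paired difference or interval, although the analysis set is paired by patient

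*Protocol*

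**What the plan says.** **Objective.** Protocol 5.1.3 sets out to "Compare the detection of local and metastatic disease using" FAPI-46 PET against a reference that includes CT and MR.

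**Protocol endpoints.** Protocol 5.2.3 has one bullet for standard of care, "Number of malignant lesions (local, metastatic) identified through anatomical (i.e., CT, MR) and/or" FDG PET. A separate bullet covers FAPI-46 "identified lesions and the radiotracer accumulation observed in local and metastatic disease using" SUV. Protocol 8.3 gives no analysis for either.

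**SAP endpoint.** SAP 6.2.3 puts both modalities in one bullet, still as a categorised count: "Number of lesions identified (0, 1, 2, 3 or more) through Standard of Care" and FAPI-46 images. SAP section 8 explains that on both image types the reader recorded the pancreas and at most three nodes judged positive. Metastatic detection is therefore no longer compared. It also says that the exact location of the nodes read on FAPI-46 is not held in the database.

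**SAP analysis.** Under SAP 10.6.5, exploratory results "will be summarized by cohort, visit, and, where applicable, by region". SAP 10.6.5.2 presents the number of nodes found by FAPI-46 versus standard of care in EFFS3, "by cohort and visit, including pre-NAT and post-NAT differences for Cohort 2". The only cross-modality statistic with an interval is in SAP 10.6.5.1, where uptake on FAPI-46 and on FDG PET in the same lesion "will be analyzed by Pearson's correlation test".

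**Analysis set.** EFFS3 (SAP 7.1.2.3) takes patients from both cohorts who "have interpretable FAPI-46 PET and standard of care images".

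**The concern.** When two imaging tests are done in the same patient, the added value of the second lies in the patients on whom they disagree. A set of counts for FAPI-46 beside a set for standard of care does not separate two quite different situations. In one, FAPI-46 finds every patient that standard of care finds, and more. In the other, each modality finds patients that the other misses. The precision of the difference also depends on that overlap. As specified, the summary leaves the comparison that the objective names to be judged by eye from two margins.

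The layout adds a practical difficulty. The schedules in both documents put baseline standard-of-care imaging at Screening and the first FAPI-46 scan at Visit 1, and SAP Table 3 keeps these as separate by-visit rows. A table by visit may therefore have no baseline row that holds both modalities.

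**Working it through.** **Plan's own figure.** There is none for this comparison. The only design figure is 92.7% power for the primary sensitivity test. It reproduces by exact binomial calculation (n = 60, reject at 51 or more positives, goal 0.75, true value 0.90: power 92.69%), and it does not bear on this point.

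**Inputs for the illustration.** The documents give no expected node counts and no size for EFFS3; 60 is its upper limit. I assume n = 60, with 26 patients node-positive on FAPI-46 and 18 on standard of care (SOC).

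**Formulas.** Let b be the patients positive on FAPI-46 only and c those positive on SOC only. The margins fix b - c = 26 - 18 = 8, but not b or c.
- Difference = (b - c)/n = 8/60 = 13.3 points.
- Paired SE = sqrt(b + c - (b - c)²/n)/n, where (b - c)²/n = 64/60 = 1.067.
- 95% CI = difference ± 1.96 × SE.
- Positive on both = 26 - b. By chance alone this would be 26 × 18/60 = 7.8.

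| FAPI-only (b) | SOC-only (c) | Both | SE | Paired 95% CI (points) |
|---|---|---|---|---|
| 8 | 0 | 18 | sqrt(8 - 1.067)/60 = 0.0439 | +4.7 to +21.9 |
| 10 | 2 | 16 | sqrt(12 - 1.067)/60 = 0.0551 | +2.5 to +24.1 |
| 18 | 10 | 8 | sqrt(28 - 1.067)/60 = 0.0865 | -3.6 to +30.3 |

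All three rows give the same counts per modality. Patients found by standard of care alone run from 0 to 10. The standard error roughly doubles (0.0865/0.0439 = 2.0), and the interval goes from excluding zero to including it.

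**Other assumed margins.** I take full nesting (c = 0) and near-chance overlap in each case.
- 54/60 and 45/60, difference 15.0 points: +6.0 to +24.0 (9 and 0), against +2.1 to +27.9 (13 and 4; both = 41, chance 54 × 45/60 = 40.5).
- 36/40 and 30/40, difference 15.0 points: +3.9 to +26.1 (6 and 0), against -1.3 to +31.3 (9 and 3; both = 27, chance 36 × 30/40 = 27).

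The spread depends on the margins, but in no case do the margins fix the discordant cells.

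**Pairing in the schedule.** Standard-of-care imaging is at Screening in both cohorts, and again at Visit 3 in Cohort 2. FAPI-46 is at Visit 1, and at Visit 3 in Cohort 2. The Table 3 footnote lets Screening or Visit 1 be renamed Baseline. SAP 9.3, however, defines baseline as the last evaluation before the first dose, and the FAPI-46 scan follows that dose, so the renaming does not clearly join the two. EFFS1 and EFFS2 say which scan is used when a patient has several; EFFS3 has no such rule. Footnote k of the Cohort 2 schedule picks the standard-of-care image nearest surgery when there are several. It words this for images taken after surgery, while placing the imaging before surgery.

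**The case against.** **It is exploratory.** Exploratory results are only summarised, and SAP 9.1 provides for testing of sensitivity. This stands, and it limits the weight of the point. But a descriptive interval is not a test, and the SAP already gives a 95% CI for another exploratory cross-modality statistic, the FDG correlation. That statistic concerns uptake, not detection.

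**A cross-table is not excluded.** A reader might infer that the trial cannot show which patients only one modality detects. The documents do not support that. The word versus in SAP 10.6.5.2 could be programmed as a cross-table, and table shells are not among the documents. Patient listings are planned for FAPI-46 results (SAP 10.6.2) and for CT/MRI with an EFFS3 marker (SAP 10.9.3), so some matching by hand is possible. It is only partial: the second listing does not name FDG PET, and the first is tied to histopathology of the same region. What stands is that nothing requires the cross-table, and no interval is planned.

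**Mixed patients within a row.** A reader might also infer that the rows generally compare different patients. In Cohort 1 there is one FAPI-46 scan and one scheduled standard-of-care time point, so membership of EFFS3 already pairs them. The doubt about which image goes with which scan is confined to Cohort 2.

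**The counts are invented.** They are, and still wider intervals can be produced only by assuming that the two modalities disagree more than chance would produce. That is implausible for two tests of the same nodes, so the working stops at near-chance overlap.

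**Conclusion.** The point holds as a gap in specification. The objective is a comparison, the data are paired by patient, and the SAP specifies only counts per modality for detection. In the main illustration the same counts fit 0 to 10 patients detected by standard of care alone, with a lower confidence limit anywhere from +4.7 to -3.6 points. Those sizes rest on assumed margins and an assumed 60 patients in EFFS3. The principle does not: margins alone determine neither the discordant patients nor the precision of the difference. The absence of a stated pairing rule is a second, smaller gap, at baseline because of the visit labels and in Cohort 2 because there are two scans. Neither gap touches the primary endpoint or its success criterion. The change is worth making because the data are already held and the stated objective otherwise has no analysis that answers it.

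**What to change.** In SAP 10.6.5.2:

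1. Define two paired time points. Baseline pairs the Screening standard-of-care image with the Visit 1 FAPI-46 scan. Post-NAT, for Cohort 2, pairs the pre-surgery standard-of-care image with the Visit 3 scan. Pair by time point and not by visit label: requiring both images at the same visit would remove all of Cohort 1 and every Cohort 2 baseline pair. Reconcile footnote k with this.
2. At each time point, among patients with both images interpretable, cross-tabulate node-positive (at least one node) on FAPI-46 against node-positive on standard of care.
3. Report the both, FAPI-only, SOC-only and neither counts, and the paired difference in proportions with a paired 95% CI. A score interval would suit discordant cells near zero better than the simple formula used above. Label the result exploratory.
4. Keep the side-by-side node counts as supplementary.
5. State that discordance shows a difference in detection, not in accuracy. State also that positive on both does not mean the same node, because node locations are not in the database. For that reason the pairing has to be by patient and not by lesion.

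The cost is SAP wording and one extra table from data already collected. Patients who lack one image at a time point leave that comparison.

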5.2.4. Safety endpoints

- Incidence and severity of TEAEs or TSEAEs 24 hours from [^{68}Ga]FAPI-46 administration according to MedDRA/CTCAE V.5.0.

6. STUDY DESIGN AND SCHEMATIC

Protocol waivers or exemptions are not allowed with the exception of immediate safety concerns. Therefore, adherence to the study design requirements, including those specified in the outline of study procedures are essential and required for study conduct.

6.1. Study Design

This is a prospective, multi-center, single arm, open label, non-randomized study to evaluate the ability of [^{68}Ga]FAPI-46 to detect FAP expressing cells in patients with resectable or borderline resectable PDAC. The [^{68}Ga]FAPI-46 PET scans will be acquired after initial staging using institutional standard methods. If the participant is prescribed neoadjuvant therapy, a second [^{68}Ga]FAPI-46 PET scan will be performed within 21 days prior to planned surgical resection. This will be followed by histopathology and IHC analyses and comparison to resected PDAC tumor specimens. The surgeon will not be blinded to the [^{68}Ga]FAPI-46 scans prior to surgery.

Experimental Design: Phase 2, prospective, multi-center, single arm, non-randomized, open label study

Allocation of treatment: open-label, non-randomized, single intervention

Number of patients planned: Up to 60 patients will be enrolled. Participants who withdraw, are withdrawn, do not complete the [⁶⁸Ga]FAPI-46 PET scan ≤ 21 days prior to surgery (Cohort 2), do not have a core biopsy prior to NAT or who are not surgical candidates post-NAT (Cohort 2) may be replaced at the discretion of the sponsor.

Summary of Study Visits and Data Collection: Refer to Schedule of Events for full requirements for each visit. The Schema provides a graphical representation of the study visits.

All participants

Screening: Screening assessments can be conducted at multiple visits provided they are within 28 days prior to study day 1, including anatomic imaging. Tests performed for standard of care may be used for screening purposes provided they are within window.

Visit 1: Defines Study Day 1. [⁶⁸Ga]FAPI-46 PET scan obtained.

Visit 2: 24 to 72 hours after [⁶⁸Ga]FAPI-46 injection. Safety assessment with safety labs and, if needed, a symptom directed physical examination. This is the last active study-related event with the participant.

Cohort 1 only: Participants in Cohort 1 are those not prescribed neoadjuvant therapy and directly undergo surgical resection within 21 days post-[⁶⁸Ga]FAPI-46 PET scan. Data will be mined from the medical records regarding the surgical procedure and pathologic outcomes. The final study-directed visit is Visit 2.

Surgery: Surgical resection to occur within 21 days after [⁶⁸Ga]FAPI-46 PET scan. Resected tissue should be collected as per laboratory manual. Surgical and pathology reports will be collected, codified, and provided for study.

Follow-up: Passive follow-up only through chart review to collect information about post-surgical imaging, planned treatment, and outcomes for 14 days following surgery.

Cohort 2 only: Participants in Cohort 2 are those who receive a tumor biopsy, are prescribed neoadjuvant therapy followed by surgical resection within 21 days after a second [⁶⁸Ga]FAPI-46 PET scan. Neoadjuvant therapy is beyond the scope of this protocol and is to be administered per standard of care by the institution and treating oncology team. Data will be mined from the medical records regarding the neoadjuvant therapy administered, surgical procedure and pathologic outcomes. The final study-directed visit is Visit 4.

Visit 3: Second [⁶⁸Ga]FAPI-46 PET scan.

Visit 4: 24 to 72 hours after [⁶⁸Ga]FAPI-46 injection. Safety assessment with safety labs and, if needed, a symptom directed physical examination.

Surgery: Surgical resection to occur within 21 days after [⁶⁸Ga]FAPI-46 PET scan. Resected tissue should be collected as per laboratory manual. Surgical and pathology reports will be collected.

Follow-up: Passive follow-up only through chart review to collect information about post-surgical imaging, planned treatment, and outcomes for 14 days following surgery.

